**Table 1 Accelerated Dose Titration Procedures**

Dose Level	Toxicity	Dose Escalation
Accelerated Dose Titration Phase		
Dose Level -1		Lower doses may be explored if DLTs or significant toxicities are observed at Dose Level 1.
Dose Level 1		Starting Dose: 3 mg daily
Subsequent Dose Levels	No subjects with either a $\geq$ Grade 2 toxicity or a DLT in first 4 weeks of treatment	Escalate to next dose level with an increase of $\leq$ 100% a
End of Accelerated Dose Titration Phase	One or more subjects with a $\geq$ Grade 2 toxicity or a DLT in first 4 weeks of treatment	Begin 3+3 dose-escalation phase

a. Dose levels in Section 4.2.1 are suggestions; the final determination of the next dose level will be made at the dose escalation meeting in concert with the Investigators, GSK Medical monitor, and representatives from Safety, Statistics, and Clinical Pharmacology. The final dose escalation decision will depend on all factors, as described in Section 11.2.1.

### 4.2.3. 3 + 3 Dose Escalation

If the accelerated dose titration ends due to  $\geq$  grade 2 toxicity then two additional subjects will be enrolled to same dose level where as, if termination of accelerated dose titration is due to DLT, then up to 5 additional subjects will be enrolled at the same dose level to continue the treatment following the 3 + 3 Dose Escalation guidelines. Subjects will be entered in a staggered approach with at least 3 days between each subject to minimize the risk of inadvertently exceeding the MTD in multiple subjects. Dose escalation decisions will be made as outlined in Table 2 Escalation to the next dose level will not increase greater than 2 fold from the previous dose level. Intra-subject dose escalation may be considered as described in Section 4.2.7. Subjects should not be enrolled at a higher dose level until at least 3 subjects in the previous dose cohort complete 4 weeks of treatment.

Dose-limiting toxicity (DLT) is based on any observed toxicity in the first 4 weeks. If 1 of 3 subjects experiences a DLT at a particular dose level, 3 additional subjects will be enrolled at that dose level. If 2 or more subjects experience a DLT at a particular dose

level, a lower (or intermediate) dose level may be explored to better define the maximum tolerated dose (MTD).

If 2 or more DLTs in 6 subjects are observed at any dose level, the MTD will have been exceeded ([Table 2](#)).

#### 4.2.4. Dose-Limiting Toxicity

An event is considered to be a dose-limiting toxicity (DLT) if the event is attributed (definitely, probably or possibly) to the study treatment during the first 4 weeks of treatment and meets the criteria described in [Table 3](#), as graded when applicable by the NCI-CTCAE v4.03.

Subjects who are unable to receive at least 75% of the scheduled doses during the 4-week DLT evaluation period will be replaced in the cohort unless the reason for the delay or discontinuation was due to a DLT.

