**Table 3 Dose –Limiting Toxicity Criteria**

Toxicity	DLT Definition
Hematologic	
 
• Grade 4 neutropenia (absolute neutrophil count [ANC] <500/mm^3 for ≥5 days)
 
• Febrile neutropenia (as defined by NCI-CTCAE v4.03 [concurrent Grade 4 neutropenia and fever >38.3°C])
 
• Grade 4 anemia of any duration
 
• Grade 3 thrombocytopenia with clinically significant bleeding or grade 4 thrombocytopenia (platelets <25,000/mm^3)
 

Non-hematologic	
 
• Alanine aminotransferase (ALT) >3x upper limit of normal (ULN) + bilirubin ≥2xULN (>35% direct) or ALT between 3-5 X ULN with bilirubin < 2xULN but with hepatitis symptoms or rash (See Section 5.4.1 for Liver Stopping Criteria)
 
• Grade 3 nausea, vomiting or diarrhea that does not improve within 24h despite appropriate supportive treatment(s)
 
• Grade 4 nausea, vomiting, or diarrhea
 
• Grade 3 hypertensioa (uncontrolled despite addition of up to 2 antihypertensive medications)
 
• Grade 4 hypertension
 
• Grade 3 or greater clinically significant non-hematologic toxicity (including QTc corrected by Fridericia's formula [QTcF]) per NCI-CTCAE, v4.03 except toxicities listed in Section 4.2.5
 
• Grade 2 troponin b elevation (central laboratory >ULN), measured on two separate occasions within 48 hours in order to confirm elevation and with other clinical signs, symptoms, laboratory tests consistent with cardiac toxicityb.
 

Other	
 
• Any toxicity resulting in a dose delay of >14 days of the intended next dose
 
• Grade 2 or higher toxicity that occurs beyond 28 days which in the judgment of the investigator and GSK Medical Monitor is considered to be a DLT
 

Toxicity Grading based on NCI-CTCAE v4.03

- a. Grade 3 hypertension adequately controlled by antihypertensive medication(s) is not considered to be a DLT.
- b. In the event a troponin (central laboratory assessment) is not performed or a laboratory error occurs, considerations for a DLT criterion will involve review of two separate local troponin (I or T) assays done within 48 hours at a local investigator site. Troponin I or T elevations greater than the upper limit of normal, and > 10% coefficient of variance (CV%) for that assay will be considered as a grade 2 elevation.

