#### Phase I/II liver chemistry stopping criteria and required follow up assessments

Liver Chemistry Stopping Criteria – Liver Stopping Event Subject with entry criteria ALT ≤ 2.5 x ULN	
ALT-absolute	ALT ≥ 5xULN
ALT Increase	ALT ≥ 3xULN persists for ≥4 weeks
Bilirubin	ALT ≥ 3xULN and bilirubin ≥ 2xULN (>35% direct bilirubin)
INR^2	ALT ≥ 3xULN and INR>1.5, if INR measured
Cannot Monitor	ALT ≥ 3xULN and cannot be monitored weekly for 4 weeks
Symptomatic	ALT ≥ 3xULN associated with symptoms (new or worsening) believed to be related to liver injury or hypersensitivity
Liver Chemistry Stopping Criteria – Liver Stopping Event Including subjects with documented liver metastases/tumor infiltration at baseline AND entry criteria ALT>2.5 x ULN but ≤5 x ULN	
ALT-absolute	Both ALT ≥ 5xULN and ≥2x baseline value
ALT Increase	Both ALT ≥ 3xULN and ≥ 1.5x baseline value that persists for ≥4 weeks
Bilirubin	ALT ≥ 3xULN and bilirubin ≥ 2xULN (>35% direct bilirubin)
INR^2	ALT ≥ 3xULN and INR>1.5, if INR measured
Cannot Monitor	Both ALT ≥ 3xULN and ≥ 1.5x baseline value that cannot be monitored for 4 weeks
Symptomatic	Both ALT ≥ 3xULN and ≥ 1.5x baseline value associated with symptoms (new or worsening) believed to be related to liver injury or hypersensitivity

Required Actions and Follow up Assessments following ANY Liver Stopping Event	
Actions	Follow Up Assessments

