
1. Serum bilirubin fractionation should be performed if testing is available. If serum bilirubin fractionation is not immediately available, discontinue study treatment for that subject if ALT  $\geq$  3xULN **and** bilirubin  $\geq$  2xULN. Additionally, if serum bilirubin fractionation testing is unavailable, **record presence of detectable urinary bilirubin on dipstick**, indicating direct bilirubin elevations and suggesting liver injury.
2. All events of ALT  $\geq$  3xULN **and** bilirubin  $\geq$  2xULN (>35% direct bilirubin) or ALT  $\geq$  3xULN **and** INR>1.5, if INR measured which may indicate severe liver injury (possible 'Hy's Law'), **must be reported as an SAE (excluding studies of hepatic impairment or cirrhosis)**; INR measurement is not required and the threshold value stated will not apply to subjects receiving anticoagulants
3. New or worsening symptoms believed to be related to liver injury (such as fatigue, nausea, vomiting, right upper quadrant pain or tenderness, or jaundice) or believed to be related to hypersensitivity (such as fever, rash or eosinophilia)
4. Includes: Hepatitis A IgM antibody; Hepatitis B surface antigen and Hepatitis B Core Antibody (IgM); Hepatitis C RNA; Cytomegalovirus IgM antibody; Epstein-Barr viral capsid antigen IgM antibody (or if unavailable, obtain heterophile antibody or monospot testing); Hepatitis E IgM antibody
5. If hepatitis delta antibody assay cannot be performed, it can be replaced with a PCR of hepatitis D RNA virus (where needed) [Le Gal, 2005].
6. Record the date/time of the PK blood sample draw and the date/time of the last dose of study treatment prior to blood sample draw on the CRF. If the date or time of the last dose is unclear, provide the subject's best approximation. If the date/time of the last dose cannot be approximated OR a PK sample cannot be collected in the time period indicated above, do not obtain a PK sample. Instructions for sample handling and shipping are in the Laboratory Manual.

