Pneumonitis	Grade 1	
 
Consider evaluation by pulmonologist. 
 
Consider room air O2 saturation at rest via pulse oximetry reading (X 2, 5 mins apart). If any decline is observed in O2 saturation,
 
 
 

Toxicity	Dose Adjustment/Stopping Criteria	Management Guidelines
		
withhold study drug, repeat chest x-ray to determine if progression of pneumonitis has occurred and consult pulmonologist.
 
 
Obtain high-resolution computed tomography (CT) scan of the chest if possible.
 

	Grade 2	
 
, then reduce dose by at least 25%.
 
Must be evaluated by pulmonologist. 
 
Consider pulmonary function tests including: spirometry, Diffusing Capacity of the Lung for Carbon Monoxide (DLCO), and weekly room air O2 saturation at rest via pulse oximetry reading (X 2, 5 mins apart). Repeat evaluations every 8-12 weeks until return to baseline.
 
Obtain high-resolution chest CT if possible.
 
Consider a bronchoscopy with biopsy and/or bronchoalveolar lavage. (BAL).
 
Treat only if symptomatic. Consider corticosteroids if symptoms are troublesome and infective origin is ruled out. Taper as medically indicated.
 
 
 
Withhold GSK2820151 until recovery to ≤ Grade 1, then reduce dose by at least 25%. Discontinue GSK2820151 if no recovery to ≤Grade 1 within 4 weeks.
 

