Thrombocytopenia	Grade 1 (platelets <LLN to $\geq 75,000/\text{mm}^3$ ) or Grade 2 (platelets <75,000 to $\geq 50,000/\text{mm}^3$ )	
 
Continue dosing at same dose level with weekly or more frequent monitoring as necessary
 

	Grade 3 (platelets <50,000 to $\geq 25,000/\text{mm}^3$ )	
 
Withhold GSK2820151 and check aPTT, PT, and INR. Monitor CBC and coagulation studies twice a week until normal, or increase monitoring frequency if clinically indicated.
 
Withhold GSK2820151 until thrombocytopenia has resolved to <math>\leq</math> Grade 2 AND aPTT, PT, and INR are all <math>\leq</math> ULN. Drug may then be restarted at a lower dose level, after discussion with the medical monitor.
 
If safety lab abnormalities recur following rechallenge, drug may be discontinued permanently or restarted at further lower dose level, after discussion with the medical monitor. If safety lab abnormalities recur to the same level following a second rechallenge, drug
 

Toxicity	Dose Adjustment/Stopping Criteria	Management Guidelines
		will be discontinued permanently.
	Grade 4 ( platelets $\leq$ 25,000) or any moderate to severe bleeding accompanied by drug related thrombocytopenia	
Withhold GSK2820151 and check aPTT, PT, and INR. Monitor CBC and coagulation studies twice a week until normal, or increase monitoring frequency if clinically indicated.
 
Withhold GSK2820151 until thrombocytopenia has resolved to <math>\leq</math> Grade 2 AND aPTT, PT, and INR are all <math>\leq</math> ULN. Drug may then be restarted at a lower dose level, after discussion with the medical monitor.
 
If safety lab abnormalities recur following rechallenge, drug may be discontinued permanently.
 
If platelet count does not recover to <math>\geq</math>25,000/mm^3 (Grade 3) within 7 days and <math>\geq</math>50,000/mm^3 (Grade 2) within 14 days, GSK2820151 should be permanently discontinued.
 
Any subject requiring transfusion support, GSK2820151 should be permanently discontinued.
 
 
•
 

All Other Toxicity*	1	
 
• Continue dosing with no change
 

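### A hold for non-bleeding Grade 3 thrombocytopenia can drop a subject from the 3+3 count with no rule requiring a DLT ruling, and ALT ≥3×ULN with INR >1.5 is not written as a DLT

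*Protocol*

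**What the plan says.** Section 4.2.4 makes an event a DLT only if it is attributed to study treatment, occurs in the first 4 weeks and meets Table 3. A subject below 75% of scheduled doses "will be replaced in the cohort unless the reason for the delay or discontinuation was due to a DLT".

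The Table 3 platelet line reads "Grade 3 thrombocytopenia with clinically significant bleeding or grade 4 thrombocytopenia". Its delay line reads "Any toxicity resulting in a dose delay of" more than 14 days. Its general Grade 3 line is limited to non-hematologic toxicity.

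Table 12 (Section 14.7.1) says for any Grade 3 thrombocytopenia: "Withhold GSK2820151 until thrombocytopenia has resolved to" Grade 2 or lower, with aPTT, PT and INR all at or below ULN as well. Treatment may then resume only at a lower dose level.

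Appendix 3 makes ALT ≥3×ULN with "INR>1.5, if INR measured" a liver stopping event that requires immediate discontinuation. Its footnote 2 groups this with the bilirubin criterion as events "which may indicate severe liver injury" (possible Hy's Law) and requires an SAE report. It adds that "the threshold value stated will not apply to subjects receiving anticoagulants". The Table 3 liver line has a bilirubin arm and a symptoms-or-rash arm but no INR arm.

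**The concern.** The platelet rules do not meet. Table 12 says that after this event the subject may not go back to the assigned dose. Section 4.2.4 can then remove the same subject from the cohort that decides whether that dose is tolerable.

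No judgment clause covers the case. The override in Section 4.2.5 applies to its own list, and its item on laboratory abnormalities controlled within 24 hours cannot describe a hold of several days. The investigator-judgment clause in Table 3 applies only beyond 28 days.

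The event is foreseeable. Section 4.6.1 reports reduced platelets and raised APTT in animals, and Section 5.4.5 sets dedicated thrombocytopenia monitoring. Table 4 admits subjects with PT/INR and PTT up to 1.5×ULN, while restart needs values at or below ULN, so a hold can outlast platelet recovery.

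At stake is the 3+3 count on which Table 2 acts. The liver omission is a separate matter: a stop that the protocol treats as possibly severe liver injury is not written as a DLT.

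**Working it through.** The plan states no figure for this point, so there is none to reproduce.

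**Dose count (exact, from Section 6.1).** Dosing days are 1, 3, 4, 5; 8–12; and 15–28, so 4 + 5 + 14 = 23 doses. 0.75 × 23 = 17.25, so 18 are needed: 17/23 = 73.9% is replaced and 18/23 = 78.3% is evaluable. Missing six doses triggers replacement. For a permanent stop, a last dose on day 22 gives 17 doses and on day 23 gives 18.

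**Holds that trigger replacement without meeting the 14-day line.** Table 3 measures delay from the intended next dose, so holds are counted from a dosing day.

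| Hold starts on | Shortest hold leaving <18 doses | Doses left after a 14-day hold |
|---|---|---|
| Days 3–5 | 8 days | 13 |
| Days 8–12 | 8 days | 11 |
| Days 15–23 | 6 days | 9, rising by 1 per day to 17 |
| Days 24–28 | none | at least 18 |

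A 14-day hold is not longer than 14 days, so each hold between these minimums and 14 days falls in the gap.

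**Chance of escalation (illustrative).** Let p be the Table 3 DLT rate, q the rate of toxicity holds or stops outside Table 3 that take dosing below 18, and a the share of those ruled DLTs. All three are assumed. With Table 2 applied automatically, the chance of escalating is (1−r)³ + 3r(1−r)⁵, where:

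- ruling made, remainder replaced: r = (p + aq)/(1 − (1−a)q); the current rule is a = 0;
- subjects kept as non-DLTs: r = p.

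For p = 0.20, q = 0.10:

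- current rule: r = 0.20/0.90 = 0.222, giving 66.0%;
- a = 0.5: r = 0.25/0.95 = 0.263, giving 57.2%;
- a = 1: r = 0.30, giving 49.4%;
- kept as non-DLTs: r = 0.20, giving 70.9%.

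| p = 0.20, q | Current rule | Half ruled DLTs | Difference (points) |
|---|---|---|---|
| 0.01 | 70.4% | 69.6% | 0.8 |
| 0.02 | 70.0% | 68.2% | 1.8 |
| 0.05 | 68.6% | 64.2% | 4.4 |
| 0.10 | 66.0% | 57.2% | 8.8 |
| 0.15 | 63.2% | 50.0% | 13.2 |

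For q from 0.05 to 0.15 with a = 0.5, escalation goes from 89.7–87.6% to 85.6–73.2% at p = 0.10, and from 46.2–39.1% to 42.8–30.1% at p = 0.30.

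**Liver.** Table 8 schedules coagulation tests inside the DLT window, so the INR criterion can be met there. An eligible subject may also be close to it at entry. Table 4 allows ALT <5×ULN with liver metastases and INR up to 1.5×ULN; if the INR ULN is 1.1 or 1.2 (assumed), that is 1.65 or 1.80.

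**The case against.** The strongest reply is that replacement is not the fault. In the example it gives 66% escalation against 71% if these subjects were kept as non-DLTs, so it is the more cautious of those two options. A reader might infer that Section 4.2.4 itself makes escalation more likely; the arithmetic does not support that. What can be criticised is the missing ruling.

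It is also fair that these events are seen. The escalation meeting reviews all available data and clinical judgment decides (Section 11.2.1). Table 2 and its footnote allow a smaller step and weigh all factors. The Safety Review Team evaluates Grade 3/4 events (Section 5.4.5). That stands: review exists and the meeting can decline to escalate. None of these provisions adds the subject to the DLT count.

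The platelet line was deliberate, added in Amendment 2 at FDA request. The documents therefore do not support reading every non-bleeding Grade 3 event as a DLT.

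The size rests wholly on assumed rates and could be small. Comparing the current rule with counting every such hold as a DLT gives a much larger gap (66% against 49% in the example), but that is not the proposed rule.

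On the liver, Table 3 cross-refers to Section 5.4.1, and rechallenge needs sponsor governance approval, separate consent and IRB approval where required. A restart within 14 days is unlikely, so the delay line may well catch the event. Table 3 does not say whether a permanent stop counts as a delay.

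Section 4.3 is permissive and concerns leaving the study for reasons other than toxicity. It is in tension with Section 4.2.4 but does not contradict it.

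**Conclusion.** The gap is real on the text and limited in reach. It needs a drug-related, non-bleeding Grade 3 platelet event, a hold of 14 days or less, and a start early enough to lose six doses. It would be wrong to infer that every 6-to-14-day hold qualifies: six days suffices only from days 15–23, eight is the minimum from dosing days 3–12, and nothing qualifies from day 24.

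The dose counts are exact. The effect on escalation is not known, because the documents give neither recovery times nor event rates. With p = 0.20 and half of such holds ruled DLTs, it is about 1–2 points at q = 0.01–0.02 and about 9 points at q = 0.10, assuming that Table 2 is applied mechanically.

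The liver omission is a mismatch between Table 3 and Appendix 3 that other Table 3 lines may partly cover.

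A reader might also infer a biased final DLT or MTD estimate. The SAP does not support that: it reports five enrolled subjects, listings only and no N-CRM analysis (Sections 1, 2.1 and 3.1). The point concerns the escalation rule as written.

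**What to change.** 1. In Section 4.2.4, state the threshold as 18 of 23 doses. Where a drug-related hold or stop takes dosing below it, require the dose-escalation meeting to rule, and document before any escalation, whether it was a DLT. If yes, count it. If no, replace the subject as now; do not keep the subject in the denominator as a non-DLT. Leave the existing exemption wording alone: widening it to any drug-related toxicity, with no ruling, would keep these subjects as non-DLTs and raise escalation (71% against 66% in the example).
2. In the Table 3 liver line, add drug-related ALT ≥3×ULN with INR >1.5. Do not apply it to subjects on anticoagulants, as in Appendix 3 footnote 2. Require worsening from baseline for subjects who enter with raised ALT or INR.

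Do not add a blanket rule that any drug-related permanent discontinuation is a DLT. It would override Section 4.2.5 for low-grade events such as fatigue or rash. Send those cases to the ruling in item 1.

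The cost is a short addition to Section 4.2.4 and one Table 3 criterion. The meeting already exists, and Section 4.2.2 already requires a written escalation rationale in the accelerated phase. The downside is an MTD that may be slightly lower or reached more slowly.

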**Table 3 Dose –Limiting Toxicity Criteria**

Toxicity	DLT Definition
Hematologic	
 
• Grade 4 neutropenia (absolute neutrophil count [ANC] <500/mm^3 for ≥5 days)
 
• Febrile neutropenia (as defined by NCI-CTCAE v4.03 [concurrent Grade 4 neutropenia and fever >38.3°C])
 
• Grade 4 anemia of any duration
 
• Grade 3 thrombocytopenia with clinically significant bleeding or grade 4 thrombocytopenia (platelets <25,000/mm^3)
 

Non-hematologic	
 
• Alanine aminotransferase (ALT) >3x upper limit of normal (ULN) + bilirubin ≥2xULN (>35% direct) or ALT between 3-5 X ULN with bilirubin < 2xULN but with hepatitis symptoms or rash (See Section 5.4.1 for Liver Stopping Criteria)
 
• Grade 3 nausea, vomiting or diarrhea that does not improve within 24h despite appropriate supportive treatment(s)
 
• Grade 4 nausea, vomiting, or diarrhea
 
• Grade 3 hypertensioa (uncontrolled despite addition of up to 2 antihypertensive medications)
 
• Grade 4 hypertension
 
• Grade 3 or greater clinically significant non-hematologic toxicity (including QTc corrected by Fridericia's formula [QTcF]) per NCI-CTCAE, v4.03 except toxicities listed in Section 4.2.5
 
• Grade 2 troponin b elevation (central laboratory >ULN), measured on two separate occasions within 48 hours in order to confirm elevation and with other clinical signs, symptoms, laboratory tests consistent with cardiac toxicityb.
 

Other	
 
• Any toxicity resulting in a dose delay of >14 days of the intended next dose
 
• Grade 2 or higher toxicity that occurs beyond 28 days which in the judgment of the investigator and GSK Medical Monitor is considered to be a DLT
 

Toxicity Grading based on NCI-CTCAE v4.03

- a. Grade 3 hypertension adequately controlled by antihypertensive medication(s) is not considered to be a DLT.
- b. In the event a troponin (central laboratory assessment) is not performed or a laboratory error occurs, considerations for a DLT criterion will involve review of two separate local troponin (I or T) assays done within 48 hours at a local investigator site. Troponin I or T elevations greater than the upper limit of normal, and > 10% coefficient of variance (CV%) for that assay will be considered as a grade 2 elevation.

#### 4.2.5. Non-Limiting Toxicities

The following toxicities have been deemed to be non-serious for the purposes of this study. These toxicities will not be taken into account for dose escalation decisions unless, in the opinion of the investigator and the GSK Medical Monitor, they represent a dose-limiting toxicity. For all other toxicities and their management, see Section 14.7.

- Grade 3 or less:
  - Fatigue
  - Rash
  - Mucositis
  - Asthenia
  - Alopecia
- Electrolyte imbalance or other laboratory abnormalities controlled within 24h

#### **4.2.6. Alteration of Schedule**

Alterations may be made to the schedule of administration and/or PK/PD sampling schedule based on the results of emerging PK and safety data.

Schedules that incorporate a recovery period may be explored (e.g., 2 weeks on, 1 week off). This approach will be considered if the safety and PK data suggest that a therapeutic exposure cannot be achieved using the initial schedule without excessive toxicity. The starting dose for the alternate schedule will be the highest completed dose level (at or below MTD) with the initial schedule. Escalation can then proceed as described using 3 + 3 dose escalation.

Schedules that use a shorter recovery period, e.g., twice daily (BID) dosing, may also be explored. This approach will be considered if the safety, PK, and emerging PD data suggest that a sufficient therapeutic exposure cannot be achieved using the initial schedule. If a shorter recovery period is used, the initial dose level will be  $\leq 50\%$  of the highest completed dose level (at or below MTD) with the initial schedule. Escalation can then proceed as described using the 3 + 3 dose escalation. Alternative schedules with intense supportive care may also be explored.

The dosing schedule may also be adjusted to expand a prior dose cohort to further evaluate safety, pharmacokinetic and/or pharmacodynamic findings at a given dose level, or to add cohorts to evaluate additional dose levels. The study procedures for these additional subject(s) or cohort(s) will be the same as that described for other study subjects.

